10.3 Additional Safety Analyses

10.3.1 Severe Ablation Complications

The proportion of subjects in each treatment group with one or more Severe Ablation Complications will be analyzed descriptively: the number with events, the total number of subjects evaluated, the percentage, and 95% Bayesian credible intervals (BCIs) for the proportion in each group as well as the difference between groups will be presented. The posterior probability that $Q_T < Q_C$ will be presented. The statistical methods will be a Bayesian comparison of proportions (with predictions) as described in Section 19. Exploratory frequentist analyses may also be conducted.

10.3.2 Nonserious / Serious CSEs

The proportion of subjects in each treatment group with any device- or procedure-related AE in the CSE definitions of the protocol (without regard for serious or non-serious categorization) will be analyzed descriptively: the number with events, the total number of subjects evaluated, the percentage, and 95% Bayesian credible intervals (BCIs) for the proportion in each group as well as the difference between groups will be presented. The posterior probability that $Q_T < Q_C$ will be presented. The statistical methods will be a Bayesian comparison of proportions (with predictions) as described in Section 19. Exploratory frequentist analyses may also be conducted.

10.3.3 Post-Blanking Cardioversions

The endpoint is Post-Blanking Cardioversions. The proportion of subjects in each treatment group with one or more Post-Blanking Cardioversions will be analyzed descriptively: the number with events, the total number of subjects evaluated, the percentage, and 95% Bayesian credible intervals (BCIs) for the proportion in each group as well as the difference between groups will be presented. The posterior probability that $Q_T < Q_C$ will be presented. The statistical methods will be a Bayesian comparison of proportions (with predictions) as described in Section 19. Exploratory frequentist analyses may also be conducted.

10.3.4 Post-Blanking Arrhythmia Hospitalizations

The endpoint is Post-Blanking Arrhythmia Hospitalizations. The proportion of subjects in each treatment group with one or more Post-Blanking Arrhythmia Hospitalizations will be analyzed descriptively: the number with events, the total number of subjects evaluated, the percentage, and 95% Bayesian credible intervals (BCIs) for the proportion in each group as well as the difference between groups will be presented. The posterior probability that $Q_T < Q_C$ will be presented. The statistical methods will be a Bayesian comparison of proportions (with predictions) as described in Section 19. Exploratory frequentist analyses may also be conducted.

10.3.5 Any Related SAE

The endpoint is Any Related SAE. The proportion of subjects in each treatment group with one or more Any Related SAEs will be analyzed descriptively: the number with events, the total number of subjects evaluated, the percentage, and 95% Bayesian credible intervals (BCIs) for the proportion in each group as well as the difference between groups will be presented. The posterior probability that $Q_T < Q_C$ will be presented. The statistical methods will be a Bayesian comparison of proportions (with predictions) as described in Section 19. Exploratory frequentist analyses may also be conducted.

10.3.6 Any Related Stroke or TIA

The endpoint is Any Related Stroke or TIA. The proportion of subjects in each treatment group with one or more Related Stroke or TIA will be analyzed descriptively: the number with events, the total number of subjects evaluated, the percentage, and 95% Bayesian credible intervals (BCIs) for the proportion in each group as well as the difference between groups will be presented. The posterior probability that $Q_T < Q_C$ will be presented. The statistical methods will be a Bayesian comparison of proportions (with predictions) as described in Section 19. Exploratory frequentist analyses may also be conducted.

10.3.7 Categorized PV Dimensional Changes

The endpoint is Categorized PV Dimensional Changes. The distribution of Categorized PV Dimensional Changes between baseline and 3 months in each treatment group will be categorized by treatment group on a per vein basis by maximal % reduction in PV diameters and computed areas into 4 groups: 0-29.9%, 30-49.9%, 50-69.9%, and $\geq 70\%$.

The number of veins with the amount of change by category, the total number evaluated, the percentage, and the results of the Fisher-Freeman-Halton test will be presented.

10.3.8 Thermal Group RF Ablation / Cryoablation Safety Assessment

The two control group technologies (radio frequency ablation and cryoablation) are to be evaluated and compared using methods analogous to the primary safety analysis, only comparing RF to Cryo groups rather than Treatment to Control. The endpoint is CSE (using the Primary Safety Endpoint Definition). The proportion of subjects with Treatment Success in each control subgroup (RF, Cryo) will be analyzed descriptively: the number with the endpoint, the total number of subjects evaluated, the percentage, and 95% Bayesian credible intervals (BCIs) for the proportion in each group as well as the difference between groups will be presented. The posterior probability that $Q_{RF} > Q_{Cryo}$ will be presented. Exploratory frequentist analyses may also be conducted.

10.3.9 Learning Curve Safety Assessment

This is an analysis of both a per-operator and a per-site learning curve in the Treatment group by enrollment sequence. Patient order will be determined by sequential procedure order by either the operator or the site, determining whether the procedure would be placed in the (1-3) group, (4-6) group, or the (>6) group.

The number of subjects with one or more CSEs by experience category, total number evaluated, the percentage, and the results of the Fisher-Freeman-Halton test for each operator and site will be presented. Supportive analyses of procedural metrics may be performed.

11 Sample Size Estimation

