**Figure 10 Rescheduled Index Procedure Blanking and Follow-Up Intervals**

## 5.6 Roll-In Subjects

Up to 105 subjects – to be treated with the FARAPULSE devices – will be consented and treated in a manner consistent with the Pulsed Field Group but will be analyzed and reported separately from the study population.

At each site, these Roll-In Subjects will be the first 1 to 3 sequentially enrolled but non-randomized subjects at that site. Sites with more than 1 Investigator will utilize available Roll-In Subjects jointly as required.

With Sponsor and Investigator agreement, the Roll-In phase at a site will be terminated at or before 3 Roll-In Subjects have been treated and all subsequent subjects at the site will be randomized as study subjects according to protocol requirements.

Roll-In Subjects will:

- Be consented using a Roll-In-specific ICF.
- Follow the Index Procedures as specified in **Section 5.2**.
- Have all study data gathered as specified in **Section 4.7.2** and **Section 4.7.3**.
- Be followed for 12 months post-ablation, completing Day 7 and Month 3, Month 6 and Month 12 Assessments for clinically-detected arrhythmias and screening for the occurrence of AEs
- Be managed according to Investigator or referring physician discretion.
- Have their required study data recorded on a specific and separate CRF set.
- Be analyzed and reported separately from the ITT Subjects.

Roll-In Subjects will not:

- Undergo Quality of Life assessments
- Undergo NAS assessment
- Undergo protocol-specified EM or Holter monitoring
- Undergo protocol-specified cardiac imaging post-procedure

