### **6.3.16 Pulsed Field Group / Subjects**

Subjects randomized to treatment with the FARAPULSE Pulsed Field Ablation System are Pulsed Field Subjects and collectively comprise the Pulsed Field Group.

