## 7.3 Additional Safety Analyses

Each of these assessments will be tested for nominal p values between Pulsed Field Subjects and Thermal Subjects:

1. **Severe Ablation Complications:** The proportion of subjects in each randomization group with one or more of the following CSE components as defined in Table 4 will be compared between treatment groups.
  - PVS
  - Persistent phrenic nerve palsy
  - Atrio-esophageal fistula
2. **Nonserious / Serious CSEs:** The proportion of subjects in each randomization group with any device or procedure-related AE in the CSE definitions table without regard for serious or nonserious categorization.
3. **Post-Blanking Cardioversions:** The proportion of subjects in each randomization group with 1 or more post-Blanking Period direct-current (electrical) cardioversions.

4. **Post-Blanking Arrhythmia Hospitalizations:** The proportion of subjects in each randomization group with 1 or more post-Blanking Period hospitalizations primarily due to arrhythmia or arrhythmia complications.
5. **Any Related SAE:** The proportion of subjects in each randomization group with any device- or procedure-related SAE.
6. **Any Related Stroke or TIA:** The proportion of subjects in each randomization group with any device- or procedure-related stroke or TIA.
7. **Categorized PV Dimensional Changes:** The distribution of PV dimensional changes between baseline and 3-month MRI/CT scans
  - a. Categorized by the % change in the PV diameters: 0-29.9%, 30-49.9%, 50-69.9% and  $\geq 70\%$  between randomization groups.
  - b. Categorized by the % change in computed cross-sectional areas: 0-49.9%, 50-74.9%, 75-89.9% and  $\geq 90\%$  between randomization groups.
8. **Thermal Group RF Ablation / Cryoablation Safety Assessment:** a descriptive comparison of safety outcomes between the two Thermal Group technologies.
9. **Learning Curve Safety Assessment:** For Pulsed Field Group only, per site and per operator learning curve assessment of the primary safety endpoint and supportive assessment of the secondary safety assessment and / or components of the CSE by enrollment sequence.

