PVI as treatment for drug-refractory paroxysmal atrial fibrillation by means of catheter ablation is recommended by the clinical community. There are two frequently used FDA-approved methods used for such ablation: radiofrequency ablation and cryoballoon technology. FARAPULSE has developed a pulsed field energy device to perform endocardial ablation that may have advantages over currently approved devices.

2 Study Design

This investigation is a prospective, randomized (1:1), adaptive, multi-center IDE pivotal study comparing the FARAPULSE Pulsed Field Ablation System to standard of care RF and cryoballoon ablation in subjects with drug-resistant symptomatic PAF.

This study is designed using Bayesian statistical methods, with non-informative prior distributions for all parameters. The appropriate sample size is determined adaptively via a Goldilocks¹⁵ design, in which the adequacy of the sample size is assessed at several pre-specified enrollment milestones.

Throughout this document, the traditional terminology “Treatment Group” (or Subjects) and “Control Group” (or Subjects) is used. These terms will refer to participants assigned to Pulsed Field or Thermal ablation therapy, respectively.

3 Analysis Objectives

The objective of this pivotal study is to provide valid scientific evidence that endocardial ablation using the FARAPULSE Endocardial Ablation System is both safe and effective for treating drug-resistant paroxysmal atrial fibrillation (PAF).

4 Analysis Populations

The population definitions in this section are copied from Section 3.4 of the protocol. Any discrepancy is inadvertent unless specifically identified as a deliberate change (or clarification) of the protocol’s definition.

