9.3.15 Learning Curve Effectiveness Assessment

This is an analysis of both a per-operator and a per-site learning curve in the Treatment group by enrollment sequence. Patient order will be determined by sequential procedure order by either the operator or the site, determining whether the procedure would be placed in the (1-3) group, (4-6) group, or the (>6) group.

The number of subjects with Acute Procedural Success by experience category, the total number evaluated, the percentage, and the results of the Fisher-Freeman-Halton test for each operator and site will be presented. The analysis will also be conducted using Treatment Success as the endpoint. Supportive analyses of procedural metrics may be performed.

10 Safety Analyses

Unless specifically identified below, all safety analyses will be performed in the Safety Population as the principal analyses. Supportive analyses will be conducted in the Per Protocol (PP) population.

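### Read literally, the learning-curve tests run site by site and operator by operator and cannot reject at an average site; one pooled analysis with a defined case number would serve better.

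*SAP*

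**What the plan says.** Two additional analyses look for a learning curve: SAP 9.3.15 (Acute Procedural Success and Treatment Success) and SAP 10.3.9 (Composite Safety Endpoint, CSE).

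- **Scope.** "This is an analysis of both a per-operator and a per-site learning curve in the Treatment group by enrollment sequence". SAP Section 2 says of the labels Treatment and Control: "These terms will refer to participants assigned to Pulsed Field or Thermal ablation therapy, respectively". Protocol 7.3 item 9 has the same limit: "For Pulsed Field Group only, per site and per operator learning curve assessment of the primary safety endpoint". Protocol 6.3.16 ties that group to randomization: "Subjects randomized to treatment with the FARAPULSE Pulsed Field Ablation System are Pulsed Field Subjects".
- **Case order.** "Patient order will be determined by sequential procedure order by either the operator or the site", giving the groups 1-3, 4-6 and above 6.
- **Test.** Counts and percentages by group are given, and "the results of the Fisher-Freeman-Halton test for each operator and site will be presented". No significance level, minimum site size, pooled test or trend model is specified.
- **Roll-Ins.** "At each site, these Roll-In Subjects will be the first 1 to 3 sequentially enrolled but non-randomized subjects at that site" (Protocol 5.6). Sites with several Investigators share them. Their outcomes are analysed apart from randomized subjects (Protocol 3.4.6 and 5.6; SAP 18.2).

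**The concern.** A learning curve is a change in outcome over an operator's or site's first few cases. Two features work against seeing it.

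First, a separate three-group exact test at each site uses only a handful of subjects. Three in each of the first two groups is the most a site can contribute there, and CSEs are expected in only about 8%. The output would be dozens of non-significant p-values that a reader could take as evidence against a learning curve, when most of the tests could not have shown one.

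Second, a site's earliest device cases are its Roll-Ins, which are not analysed here, and the SAP leaves the numbering of the remaining cases open. The label 1-3 could therefore mean different amounts of experience at different sites.

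**Working it through.** **The plan's own figures.** The documents give no power or sample size for these tests. The inputs come from the sizing of primary safety in SAP 11.1. The Farrington-Manning formula with CSE 0.08 in both groups, margin 0.08, one-sided 0.05 and 90% power gives 213.3, hence 214 per group and 428 in total. 428/0.95 = 450.5, against 450 stated. The 8% design rate is used below.

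**Subjects per site.** Up to 35 sites (Protocol 4.5), 1:1 allocation (Protocol 9.2), N from 350 to 750 (SAP 12). Average Pulsed Field subjects per site = (N/2)/35:

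- N=350: 175/35 = 5.0; expected CSEs 5.0 × 0.08 = 0.40
- N=450: 225/35 = 6.4; expected CSEs 0.51
- N=750: 375/35 = 10.7; expected CSEs 0.86

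The 45-subject site cap allows about 22 or 23 Pulsed Field subjects. At N=750 the cap is 10%, or 75 subjects, about 38 of them Pulsed Field. Per-operator counts are smaller wherever a site has several operators.

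**Smallest attainable p.** For a fixed number of events, the p-value sums the probabilities of all tables no more likely than the one observed. The most extreme cases are:

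- 3+2, two events both in the group of 2: 1/C(5,2) = 1/10 = 0.10
- 3+3, three events all in one group: 2 × 1/C(6,3) = 2/20 = 0.10
- 3+3+1, three events all in one group of 3: 2 × 1/C(7,3) = 2/35 = 0.057

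All exceed 0.05. A site with 5 to 7 Pulsed Field subjects therefore has exactly zero power at 0.05 for either endpoint. This needs no assumed effect.

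**Larger sites.** Exact enumeration of all 3×2 tables at an assumed two-sided 0.05. The patterns across the three order groups are assumptions:

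| Assumed pattern | 3/3/4 | Site near the 45 cap | 3/3/32 (75 cap) |
|---|---|---|---|
| CSE 16/8/8% | 0.4% | 3.2% (3/3/17) | 5.7% |
| CSE 24/8/4% | 1.2% | 10.1% (3/3/17) | 16.7% |
| CSE 25/12/6% | 1.4% | 10.5% (3/3/16) | not run |
| Treatment Success 50/65/65% | 4.0% | 6.8% (3/3/17) | 6.3% |
| Treatment Success 35/55/70% | 9.4% | 18.5% (3/3/17) | 19.9% |

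**Pooled over sites.** Two-sided Cochran-Armitage trend test, scores 0, 1, 2, on 225 Pulsed Field subjects (N=450) with an assumed split of 90/75/60, by simulation:

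- CSE 12.8/6.2/3.1%: about 63%
- CSE 12/7/4%: about 44%
- CSE 16/8/8%: about 38%
- CSE 25/12/6%: about 92%, but the overall rate is (22.5 + 9 + 3.6)/225 = 15.6%, nearly twice the design rate. Scaling by 8/15.6 gives the 12.8/6.2/3.1% row.

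Hand check for 16/8/8%: the overall rate is 25.2/225 = 0.112. The expected trend statistic is (75×0.08 + 2×60×0.08) − 0.112×195 = 15.6 − 21.84 = −6.24. Its null SD is √(0.112 × 0.888 × (315 − 195²/225)) = √(0.0995 × 146) = 3.81. The ratio is 1.64, so power is about Φ(1.64 − 1.96) = 37%.

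**Case numbering.** Suppose a site has r Roll-Ins, with r from 1 to 3. If Roll-Ins are not counted, group 1-3 holds the site's device cases r+1 to r+3: 2-4, 3-5 or 4-6. If they are counted, group 1-3 holds only 3 − r randomized cases: 2, 1 or none.

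**The case against.** The strongest reply is that the test wording can be read another way: one table with experience defined by operator and one with it defined by site, each pooled over the trial. That fits the opening sentence of both sections. The authors also knew that tests at tiny sites are uninformative, since SAP 17 drops sites with fewer than 8 subjects from inferential poolability tests. On this reading the power criticism largely falls: a pooled Fisher-Freeman-Halton table with an assumed 90/90/45 split has about 36% power for CSE 16/8/8% and 93% for 24/8/4%. The reply stands as a reason to clarify. It does not settle the matter, because the literal wording is a test for each operator and site, and neither section carries over the small-site exclusion.

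Several stronger readings are tempting and not supported:

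- *Counting begins after the Roll-Ins.* The SAP restricts who is analysed; it does not say where the sequence starts.
- *All earliest cases are missed.* This is true of each site's first cases. Roll-Ins are shared, so an operator who had none has a true first case in the per-operator analysis. Roll-In outcomes are also reported separately.
- *The trial will conclude that there is no learning curve.* Counts and percentages by group are presented too, supportive procedural analyses are allowed, and no decision depends on these p-values.
- *Training needs are a stated question.* The documents pre-specify the assessments without giving that purpose.
- *Pooling gives over 90% power.* For the trend test that needs an overall CSE rate of 15.6%, close to the 16% that SAP 14 uses as the safety null.

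**Conclusion.** The concern holds as a minor one. On the literal reading, the test at an average site cannot reach 0.05 at N=350 or N=450, and it has low power even at sites at the enrolment cap. The zero-power result rests on 35 active sites and a 0.05 level, which the SAP does not state. With fewer sites the average rises: 25 sites give 7.0 subjects at N=350, still zero power, but 225/25 = 9.0 at N=450, where rejection becomes possible. The percentages for larger sites also rest on assumed patterns.

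Separately, the meaning of case number is undefined, and each site's first 1 to 3 device cases are outside the analysis on either reading.

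Pooling is clearly better but no guarantee: for 16/8/8% it moves power from 0.4% (3/3/4) or 3.2% (3/3/17) to about 38%. These pooled figures use an assumed split by randomized order and ignore variation between sites. Power under true case numbers was not computed. The primary safety and effectiveness conclusions are not touched.

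**What to change.** In SAP 9.3.15 and 10.3.9:

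1. Replace the separate tests with one analysis per endpoint, pooled over all randomized Pulsed Field subjects. Examples are a trend test or a logistic mixed model on case number with a random intercept for operator or site. Run it once with operator-level and once with site-level experience. Show per-site and per-operator counts descriptively, without p-values.
2. Define case number over all Pulsed Field procedures by that operator or site, Roll-Ins included, so that randomized cases carry their true position. Because group 1-3 can then be empty at a site with three Roll-Ins, use case number itself rather than the three groups.
3. Optionally, show Roll-In results alongside for Acute Procedural Success and the 7-day CSE components only. Do not extend this to pulmonary vein stenosis or Treatment Success: under Protocol 5.6, Roll-Ins have no protocol-specified post-procedure cardiac imaging and no event or Holter monitoring, so those outcomes would be under-detected in the earliest cases.

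Items 1 and 2 need only SAP text. They keep the analysed set that Protocol 7.3 and 7.6 specify and take only a procedure count from the Roll-Ins, whose outcomes stay separate. The sponsor should confirm that the operator is recorded for Roll-In procedures. The price is that no individual site or operator is tested any longer.

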11.1 Safety Estimation

Although the pre-specified statistical analysis methods are Bayesian, standard frequentist considerations are used to guide sample size selection. The sample size for primary safety computed for a Farrington-Manning test with PASS 13¹¹ indicates that, for 1:1 randomization, 90% power, alpha=0.05 (one-sided), CSE rate in both Groups of 0.08 and non-inferiority margin of 0.08, the study requires a completed sample size of 214 subjects in each Group, for a total of 428. Assuming a 5% rate of loss-to-follow-up (LTFU), 450 subjects are needed.

There is uncertainty in the CSE rate, and this can have dramatic impact on sample size requirements. If the CSE rate is 0.07 in the Pulsed Field group but 0.08 in the Thermal group, 326 subjects are required to achieve 90% power (344 after compensating for 5% LTFU). If the CSE rate is 0.10 in the Pulsed Field group but 0.08 in the Thermal group, 690 subjects are required to achieve 85% power (727 after compensating for 5% LTFU). Interim analyses can also increase the sample size requirement. This uncertainty in the CSE rate motivates the use of a design wherein the sample size is adaptively determined, with possible sample sizes ranging from 350 to 750.

Overall statistical power for the study depends on power for the primary effectiveness test as well as the primary safety test. Power is more thoroughly estimated by simulation and is described in Section 14.

11.2 Effectiveness Estimation

Although the pre-specified statistical methods are Bayesian, standard frequentist considerations are used to guide sample size selection. The sample size required for the primary effectiveness endpoint obtained by PASS 13¹¹ for 1:1 randomization, 90% power, alpha=0.05 (one-sided), success rates in each group of 0.65 and non-inferiority margin $\delta=0.15$ is 172 subjects in each arm, for a total of 344 subjects. Similar to the safety objective, there is uncertainty in the success rates, especially in the Pulsed Field group. If the success rate in the Pulsed Field group is 0.625 but 0.65 in the Thermal group, 502 subjects are required to achieve 90% power (558 after compensating for up to 10% missing data). If the success rate in the Pulsed Field group is 0.70 but 0.65 in the Thermal group, only 186 subjects are required to achieve 90% power (207 after compensating for missing data). Interim analysis can also increase the sample size requirement. This uncertainty in the Treatment Success rate motivates the use of a design wherein the sample size is adaptively determined, with possible sample sizes ranging from 200 to 550. This overlaps with the range computed for Safety Estimation, but it is expected that the primary safety objective will be the primary driver of sample size; therefore, the minimum possible sample size for this study is set to 350, and the maximum is set to 750.

Overall statistical power for the study depends on power for the primary effectiveness test as well as the primary safety test. Power is more thoroughly estimated by simulation and is described in Section 14.

Number of Enrolled Subjects:

The primary population for the analysis of effectiveness is the MITT Population. The Safety Population should be similar but will not be smaller. Considering the joint sample size needs of the primary safety and effectiveness objectives, the primary effectiveness analysis population may range from a minimum of 350 to a maximum of 750.

To achieve a sample size of 750 MITT Subjects, up to 900 subjects may be enrolled, consisting of 750 MITT and up to 105 Roll-In and up to 45 Randomized Subjects (6%) who do not meet the criteria for the MITT Population. See Section 4.1.

12 Analysis Plan

This trial includes interim analyses for the purpose of determining sample size and possibly stopping enrollment. Once enrollment has stopped, all subjects will be followed for 12 months, and then the primary analysis will occur. There is no interim test of the primary hypotheses.

One blinded administrative analysis will occur when 100 randomized subjects have completed 7 days of follow-up. The analysis of adverse events, Acute Procedural Failure and Chronic Failure will be aggregated across treatment groups and will not examine between-group differences in any fashion. The aggregated results will be used to assess consistency of early outcomes with the parameter assumptions underlying the design of the ADVENT Trial, in support of clinical trial submissions to regulatory authorities in other countries. This analysis is not part of the formal sequential, adaptive plan.

This trial is designed using Bayesian statistical techniques. The appropriate sample size is determined adaptively via a Goldilocks design¹⁵, with possible sample sizes of N=350, 450, 550, 650, and 750.

The sample size determination algorithm is as follows. At a pre-defined interim analysis point (e.g., when $N=N_i$ subjects have been accrued into the MITT population; $N_i = 350, 450, 550$ and 650), four predictive probabilities are calculated:

- $PP_{int,saf}$ = Predictive probability that the trial will establish non-inferiority for safety, once the current sample (N_i) is followed to 12 months.
- $PP_{max,saf}$ = Predictive probability that the trial will establish non-inferiority for safety, assuming the maximum sample size (750) is attained and followed to 12 months.
- $PP_{int,eff}$ = Predictive probability that the trial will establish non-inferiority for effectiveness, once the current sample (N_i) is followed to 12 months.
- $PP_{max,eff}$ = Predictive probability that the trial will establish non-inferiority for effectiveness, assuming the maximum sample size (750) is attained and followed to 12 months.

If $PP_{int,saf}$ exceeds a suitably high threshold $W_{saf,i}$, and if $PP_{int,eff}$ exceeds a suitably high threshold $W_{eff,i}$, accrual of subjects will stop because final success looks probable with the current sample. On the other hand, if $PP_{max,saf}$ is less than a suitably low threshold $F_{saf,i}$, or if $PP_{max,eff}$ is less than a suitably low threshold $F_{eff,i}$, subject accrual will stop because final success is unlikely. In either case, follow-up continues to 12 months for all subjects, at which time the final analysis will occur. If neither of these conditions obtains, enrollment will continue to the next larger sample size (subject to the maximum of 750). These analyses are termed "Interim Sample Size Looks."

Table 1 displays the thresholds against which the predictive probabilities above are compared.

Table 1 Posterior Probability Thresholds for Stopping Accrual

Interim Sample Size Look	Effectiveness		Safety	
	Promise Threshold $W_{eff,i}$	Futility Threshold $F_{eff,i}$	Promise Threshold $W_{saf,i}$	Futility Threshold $F_{saf,i}$
N=350	0.95	0.05	0.95	0.05
N=450	0.90	0.10	0.90	0.10
N=550	0.85	0.10	0.85	0.10
N=650	0.80	0.10	0.80	0.10

Once subject accrual has stopped, all accrued subjects will be followed to 12 months, and then the inferential tests of non-inferiority described in Sections 9.1 and 10.1 will occur. This is the only time that non-inferiority is tested.

13 Imputations and the Predictive Model

This section describes the prediction model that is used to impute the 12-month outcomes for subjects who have not yet reached 12 months. This model computes Bayesian posterior predictive probabilities and serves as the basis for the predictive probability of future trial success that is computed at the interim sample size looks. With a slight change to the specification of a prior distribution, a nearly identical model serves as the “imputer’s model” in a Bayesian multiple imputation that is used to account for missing data in the final inferential tests of the primary endpoints.

